8.8.5 Handling of participants after temporary treatment discontinuation

Temporary discontinuation of LIRA 3mg may be considered by the PI because of suspected Adverse Events (AEs). A rationale (e.g. severe nausea and vomiting, other gastrointestinal symptoms) must be given in writing by the PI.

Re-initiation of treatment with LIRA 3mg may be done at a lower dose, under close and appropriate clinical/and or laboratory monitoring once the PI has considered, according to their best medical judgment, that the possible responsibility of the LIRA 3mg in the occurrence of the concerned event was unlikely and if the inclusion and exclusion criteria for the study are still met.

For all temporary treatment discontinuations, the duration of treatment discontinuation should be recorded by the research team when considered as confirmed.

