9.4 Compliance with Study Treatment

All participants in the study who have been prescribed LIRA 3mg should administer the drug daily. The participants will be instructed to return all unused, used or part-used medication/vials and packaging from used medication at each visit. Adherence questions will also be asked in follow-up visits for participants on LIRA 3mg. Examining medication returns and evaluating adherence will allow for an assessment of compliance and drug accountability. All participants should report all events which they believe may have impact on dose adjustment (such as nausea, vomiting). The Investigator may withdraw the participants if they consider dose compliance is unsatisfactory. Participants will be defined as treatment compliant if they take 70% of planned doses.

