Overall hypoglycaemia rate – ADA definition	52, 104	Hypoglycaemia events will be defined as per Appendix 5 for people without

		diabetes and as per the ADA definition in Appendix 5 for people with diabetes. Hypoglycaemia rate will be calculated per participant as total number of hypoglycaemia events divided by the total follow-up time.
Overall hypoglycaemia rate – Novo Nordisk	52, 104	Hypoglycaemia events will be defined as per Appendix 5 for people without diabetes and as per the Novo Nordisk definition in Appendix 5 for people with diabetes. Hypoglycaemia rate will be calculated per participant as total number of hypoglycaemia events divided by the total follow-up time.
AEs	Continual	Defined as in protocol with MEDRA coding used to classify AEs into System Organ Classes
SAEs	52, 104	Defined as in protocol with MEDRA coding used to classify SAEs into System Organ Classes
Rates of severe hypoglycaemia	52, 104	Calculated per participant as total number of severe hypoglycaemia events divided by the total follow-up time, where severe hypoglycaemia is defined as hypoglycaemic episodes requiring the assistance of another person to actively administer carbohydrate, glucagon, or other resuscitative actions (i.e., 'severe hypoglycaemic episodes')
Change in heart rate from baseline (beats per minute)	52, 104	Follow-up heart rate – baseline heart rate
Compliance of patient with the treatment		
Compliant with Tier 3 service (completers)	52, 104	Binary indicator of 1 if participant is compliant, 0 otherwise (defined in study database)
Stopped treatment with LIRA 3mg because of adverse effects	52, 104	Binary indicator of 1 if participant stopped treatment with LIRA 3mg because of adverse effects*, 0 otherwise. Only defined for participants in intervention arm who were currently eligible for LIRA 3mg treatment. * This includes main reason of 'adverse event' or 'unable to tolerate drug'.
The adherence of participants with the LIRA	52, 104	Participants will be defined as treatment compliant if they self-administer at least 70% of planned doses. Binary indicator of 1 if participant is compliant, 0 otherwise.

3mg (monitored through specific questionnaire and return of used pens)		Given the change in visits as a result of COVID-19 to allow face-to-face, this will be defined using the questionnaire answers as detailed in Appendix 7. Only defined for participants in intervention arm who were currently eligible for LIRA 3mg treatment.

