Total Leisure-Time MET-minutes/week = sum of Walking + Moderate + Vigorous MET-minutes/week scores in leisure.

Total Scores for all Walking, Moderate and Vigorous Physical Activities

Total Walking MET-minutes/week = Walking MET-minutes/week (at Work + for Transport + in Leisure)

Total Moderate MET-minutes/week total = Moderate MET-minutes/week (at Work + Yard chores + inside chores + in Leisure time) + Cycling Met-minutes/week for Transport + Vigorous Yard chores MET-minutes/week

Total Vigorous MET-minutes/week = Vigorous MET-minutes/week (at Work + in Leisure)

Note: Cycling MET value and Vigorous garden/yard work MET value fall within the coding range of moderate-intensity activities.

Total Physical Activity Scores

An overall total physical activity MET-minutes/week score can be computed as: Total physical activity MET-minutes/week = sum of Total (Walking + Moderate + Vigorous) METminutes/week scores.

This is equivalent to computing: Total physical activity MET-minutes/week = sum of Total Work + Total Transport + Total Domestic and Garden + Total Leisure-Time MET-minutes/week scores.

As there are no established thresholds for presenting MET-minutes, the IPAQ Research Committee proposes that these data are reported as comparisons of median values and interquartile ranges for different populations.

14 Appendix 7 Definitions for adherence of participants with the LIRA 3mg

Individuals that didn't receive 70% of the doses as determined by the protocol (i.e. in the first 16 weeks or there after whilst continuing to meet the continue rules of the protocolised treatment schedule) will be classed as not adhering with the LIRA 3mg pathway.

Defining days taking LIRA

The number of days taking LIRA will be calculated as the time from first dose dispensed (normally at baseline visit) to the last known date of individuals taking the LIRA. Where individuals are recorded as not completing the trial due to stopping the LIRA, the date of last dose of LIRA in the completion form will be used; if this is not recorded then the date of first visit at which individuals say they are not happy to continue taking LIRA will be used; and where neither of these are recorded the date of the last visit that individuals said they are happy to continue LIRA will be used.

14.1 52 weeks

Individuals will then be assessed for whether they have received 70% as per table below.

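### SAP Appendix 7 counts a resumed pause in liraglutide as treatment, so a participant who took under 70% of planned doses can pass the per-protocol dose test

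*SAP*

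**What the plan says.** The criterion is a share of doses. Protocol 9.4 states: "Participants will be defined as treatment compliant if they take 70% of planned doses". SAP 2.2.1 repeats it for the adherence outcome: "Participants will be defined as treatment compliant if they self-administer at least 70% of planned doses". The per-protocol definitions in Protocol 11.5 and SAP 3.3.3 also require at least 70% of planned doses. Dosing is once a day: "All participants in the study who have been prescribed LIRA 3mg should administer the drug daily" (Protocol 9.4).

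The operational rule is in SAP Appendix 7 (section 14). Its key sentence reads: "number of days taking LIRA will be calculated as the time from first dose dispensed (normally at baseline visit) to the last known date", meaning the last date on which the participant is known to have taken the drug. Tables 14.1 and 14.2 compare that figure with 70% of all days from baseline to week 16, 32, 52 or 104, depending on how far the stopping rules let the participant continue. If the visit date is missing, fixed cut-offs of 78, 156, 254 and 510 days apply. SAP 3.3.3 sends the per-protocol dose test to these tables.

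Protocol 8.8.5 provides for temporary discontinuation and restart, possibly at a lower dose, and says that "the duration of treatment discontinuation should be recorded by the research team". Protocol 8.8.4 treats permanent discontinuation as a last resort. Protocol 9.1 gives a second route, suspension around a contra-indicated procedure. SAP 2.2.1 explains the use of a proxy by the COVID-19 changes to visits: "this will be defined using the questionnaire answers as detailed in Appendix 7".

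**The concern.** With daily dosing, elapsed time equals doses taken only if there is no gap. The protocol foresees gaps, but Appendix 7 deducts none. A participant who is back on treatment at the visit scores 100% however long the pause was. Two participants who took the same number of doses can therefore fall on opposite sides of the 70% line, depending only on whether the untaken doses came before a restart or after a final stop.

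Three results use the rule: the LIRA adherence outcome, which SAP 5.5.1 leaves descriptive; the per-protocol analysis of the primary outcome, a secondary analysis in SAP 5.4.2; and the exploratory analysis in SAP 5.4.4, which starts from the per-protocol set. The dose test applies only to the intervention arm, so any misclassification falls on one side of the per-protocol comparison. The primary complete-case analysis and the ITT analysis do not use Appendix 7 and are unaffected.

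**Working it through.** **Inputs.** One dose per day (Protocol 9.4); threshold 70% (Protocol 9.4, SAP 2.2.1 and 3.3.3); numerator and denominator as in SAP Appendix 7; periods of 16, 32, 52 and 104 weeks, so D = 112, 224, 364 and 728 days. Dispensing is taken to be at baseline.

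**1. The SAP's own cut-offs.** The largest whole number of days below 0.70 × D:

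| Week | D | 0.70 × D | Largest value below | SAP cut-off |
|---|---|---|---|---|
| 16 | 112 | 78.4 | 78 | 78 |
| 32 | 224 | 156.8 | 156 | 156 |
| 52 | 364 | 254.8 | 254 | 254 |
| 104 | 728 | 509.6 | 509 | 510 |

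The first three reproduce. The last is one day high (510/728 = 70.05%), a separate small slip.

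**2. Smallest pause that breaks the dose criterion.** If the participant is on LIRA at the visit, the SAP score is D/D = 100%. The share of doses taken is (D − p)/D for a total pause of p days. The smallest p giving less than 0.70 is:

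- week 16: 112 − 78 = 34 (78/112 = 69.6%)
- week 32: 224 − 156 = 68 (156/224 = 69.6%)
- week 52: 364 − 254 = 110 (254/364 = 69.8%)
- week 104: 728 − 509 = 219 (509/728 = 69.9%)

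**3. Range over the visit windows.** The denominator runs to the actual visit, so p moves with it: 30 to 38 days at week 16 (day 98 to 126), 64 to 72 at week 32 (day 210 to 238), 82 to 137 at week 52 (day 273 to 455, taking 3 months as 91 days) and 215 to 223 at week 104 (day 714 to 742).

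**4. Same doses, different class.** Take two participants, both in the first row of table 14.1 (continuation rule not met at week 16). One stops for good at day 70: 70/112 = 62.5%, not adherent. The other pauses for 42 days and resumes to day 112. Doses taken are 112 − 42 = 70, again 62.5%, but the score is 112/112 = 100%, adherent.

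**5. Why a correction needs a cap.** A participant is dosed to day 728 with a 140-day pause in year 1. Subtracting the pause from the uncapped span gives 728 − 140 = 588 days, which passes the week-52 test (254.8 days). Capped at day 364 the result is 364 − 140 = 224, and 224/364 = 61.5%, which fails.

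**The case against.** The strongest defence is that a pause sanctioned under Protocol 8.8.5 is part of the prescribed pathway, so those days should not count against the participant. A per-protocol set that tolerated such pauses would be defensible, but it is not what the SAP defines. Paused days stay in the denominator as planned days, and a permanent stop at day 70 is scored non-adherent even if the investigator directed it. SAP 5.8 declares no move from doses to elapsed time.

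A second defence is that the proxy is disclosed. It is, and COVID-19 explains relying on questionnaire answers. It does not explain leaving out pauses whose length the protocol asks sites to record.

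A third is that the case is narrow, and this stands. The pause must exceed 30% of the period. Restart under 8.8.5 requires a judgement that "the possible responsibility of the LIRA 3mg in the occurrence of the concerned event was unlikely" and that eligibility still holds. Intolerance leads to withdrawal from the drug, and investigators may withdraw participants for poor dose compliance. The later rows are reached only after at least 10% weight loss at week 32, and for the week-104 row at least 15% at week 52. The participant must also meet the Tier 3 contact rule and the other per-protocol conditions. The number affected could be zero.

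A reader might infer that the rule errs equally in the other direction, because in one fallback the "date of first visit at which individuals say they are not happy to continue taking LIRA will be used" as the end date, even if dosing later restarted. That fallback covers only participants recorded as not completing the trial because they stopped LIRA, with no last-dose date on the completion form. Needing a documented restart as well makes it too contrived to carry the point.

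**Conclusion.** The point holds as a mismatch between the stated criterion and its derivation. A participant who pauses for more than 30% of the planned period and is back on LIRA at the assessment is scored 100% adherent and passes the per-protocol dose test, despite taking fewer than 70% of planned doses. The thresholds are 34, 68, 110 and 219 days at nominal visit dates. They rest on daily dosing, dispensing at baseline and no other missed doses.

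A reader might go further and infer that the per-protocol estimate is materially biased. The documents do not support that: they give no pause rate, and the effect is confined to one descriptive outcome, one secondary analysis and one exploratory analysis. The change should be made, but the main conclusion does not depend on it.

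**What to change.** In SAP Appendix 7:

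1. Cap the span at the relevant assessment date (week 16, 32, 52 or 104).
2. Subtract documented temporary-discontinuation days that can be placed within the capped span, using recorded pause dates or, failing those, the recorded duration and the visit at which it was entered.
3. Apply the existing 70% thresholds to the result, both for the adherence outcome and for per-protocol membership.

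Protocol 8.8.5 asks only for the duration of a pause, so dates may not exist. If durations or their timing were not captured, state this in SAP 5.8 and label the measure time on treatment, not doses taken.

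The cost is one or two sentences and a short extra derivation. The SAP is marked as a draft and is to be finalised before database lock, so the change is still possible under its own terms. There is one real downside: undocumented missed doses remain uncounted, so a documented pause would be penalised while the same number of silent misses would not. The write-up should say so.

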3.3.3 Per Protocol Population

The per protocol population is defined as all participants who were compliant with their randomised treatment group, analysed according to the treatment group to which they have randomised at baseline. Participants in the standard care group are defined as treatment compliant if they complete at least 70% of the planned contacts in the Tier 3 service. Participants in the intervention group are defined as treatment compliant if they complete at least 70% of the planned contacts in the Tier 3 service, and take at least 70% of their planned doses of LIRA 3mg as stipulated by the prescribing pathway.

Participants that had Liraglutide 3mg outside of the treatment pathway (i.e. in the control group or in the intervention group after a stopping rule means they should have stopped taking Liraglutide 3mg) will be excluded from the per protocol population. The protocol deviations and in particular deviations from randomised treatment group in the protocol deviations will capture where this has occurred for any individual.

Participants who had bariatric surgery during the study period will be only be included at time-points prior to their bariatric surgery. They will be excluded from time-points after their bariatric surgery.

The binary variable of compliant with tier 3 service at 52 weeks will be used to exclude individuals that did not have 70% of planned visits for outcomes assessed at 52 weeks, likewise for outcomes assessed at 104 weeks the variable at 104 weeks will be used.

Individuals in the intervention arm that did not receive 70% of the doses as determined by the protocol (i.e. in the first 16 weeks or there after whilst continuing to meet the continue rules of the protocolised treatment schedule) will be excluded from the per protocol populations. The number of days taking LIRA and whether this corresponds to 70% of doses is defined in Appendix 7 in section 14. For outcomes at

the 52 week time point the definition in 14.1 should be used; while for outcomes at the 104 week time point the definition in 14.2 should be used.

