Stopping rule on protocolised treatment schedule	Did not receive 70% of planned doses	Did receive 70% of planned doses
Did not meet rule to continue on Lira at 16 weeks (either <5% weight loss or not measured)	If days taking LIRA is <70% of days between baseline and Week 16. Or, if Week 16 date missing, if days taking LIRA is ≤ 78 .	If days taking LIRA is $\geq 70\%$ of days between baseline and Week 16. Or, if Week 16 date missing, if days taking LIRA is >78
Did meet rule to continue Lira ($\geq 5\%$ weight loss) at 16 weeks but did not meet rule to continue Lira at 32 weeks (either <10% weight loss or not measured)	If days taking LIRA is <70% of days between baseline and Week 32. Or, if Week 32 date missing, if days taking LIRA is ≤ 156 .	If days taking LIRA is $\geq 70\%$ of days between baseline and Week 32. Or, if Week 32 date missing, if days taking LIRA is >156 .
Did meet rule to continue Lira ($\geq 5\%$ weight loss) at 16 weeks and did not meet rule to continue Lira at 32 weeks ($\geq 10\%$ weight loss)	If days taking LIRA is <70% of days between baseline and week 52. Or, if week 52 date missing, if days taking LIRA is ≤ 254 .	If days taking LIRA is $\geq 70\%$ of days between baseline and week 52. Or, if week 52 date is missing, if days taking LIRA is >254 .

14.2 104 weeks

Individuals will then be assessed for whether they have received 70% as per table below.

Stopping rule on protocolised treatment schedule	Did not receive 70% of planned doses	Did receive 70% of planned doses
Did not meet rule to continue on Lira at 16 weeks (either <5% weight loss or not measured)	If days taking LIRA is <70% of days between baseline and Week 16. Or, if Week 16 date missing, if days taking LIRA is ≤ 78 .	If days taking LIRA is $\geq 70\%$ of days between baseline and Week 16. Or, if Week 16 date missing, if days taking LIRA is >78
Did meet rule to continue Lira ($\geq 5\%$ weight loss) at 16 weeks but did not meet rule to continue Lira at 32 weeks (either <10% weight loss or not measured)	If days taking LIRA is <70% of days between baseline and Week 32. Or, if Week 32 date missing, if days taking LIRA is ≤ 156 .	If days taking LIRA is $\geq 70\%$ of days between baseline and Week 32. Or, if Week 32 date missing, if days taking LIRA is >156 .

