Did meet rule to continue Lira ($\geq 5\%$ weight loss) at 16 weeks, did meet rule to continue Lira at 32 weeks ($\geq 10\%$ weight loss) and did not meet rule to continue Lira at 52 weeks (either <15% weight loss or not measured)	If days taking LIRA is <70% of days between baseline and week 52. Or, if Week 52 date missing, if days taking LIRA is ≤ 254 .	If days taking LIRA is $\geq 70\%$ of days between baseline and week 52. Or, if Week 52 date missing, if days taking LIRA is >254 .
Did meet rule to continue Lira ($\geq 5\%$ weight loss) at 16 weeks, did meet rule to continue Lira at 32 weeks ($\geq 10\%$ weight loss) and did meet rule to continue Lira at 52 weeks ($\geq 15\%$ weight loss)	If days taking LIRA is <70% of days between baseline and week 104. Or, if Week 104 date missing, if days taking LIRA is ≤ 510 .	If days taking LIRA is $\geq 70\%$ of days between baseline and week 104. Or, if Week 104 date missing, if days taking LIRA is >510 .

15 Appendix 8: Baseline and follow-up Glycaemic Status Definitions

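### SAP Appendix 7, table 14.1: the third row contradicts itself on the week-32 rule, so participants who met both continuation rules have no 52-week adherence row

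*SAP*

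**What the plan says.** SAP 2.2.1 sets the adherence threshold: "Participants will be defined as treatment compliant if they self-administer at least 70% of planned doses". It refers to Appendix 7 for the derivation. SAP 3.3.3 uses the same appendix to build the per-protocol population and assigns the tables by visit: "the 52 week time point the definition in 14.1 should be used; while for outcomes at the 104 week time point the definition in 14.2".

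Table 14.1 (52 weeks) has three rows:

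- Row 1: week-16 rule not met. Days on LIRA are judged against the time from baseline to week 16.
- Row 2: week-16 rule met, "but did not meet rule to continue Lira at 32 weeks (either <10% weight loss or not measured"). Days are judged against week 32.
- Row 3: week-16 rule met "and did not meet rule to continue Lira at 32 weeks", followed by a bracket giving weight loss of at least 10%. Days are judged against week 52: "If days taking LIRA is <70% of days between baseline and week 52".

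Table 14.2 (104 weeks) has four rows. Rows 3 and 4 are for people who "did meet rule to continue Lira at 32 weeks", with the same bracket of at least 10%. Row 3 has the same week-52 denominator and the same 254-day fallback as row 3 of 14.1.

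Each row also has a fallback in days for use when the visit date is missing: 78 (week 16), 156 (week 32), 254 (week 52) and, in row 4 of 14.2, 510: "Or, if Week 104 date missing, if days taking LIRA is" at most 510, the participant is classed as not having received 70%.

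**The concern.** In 14.1, rows 2 and 3 both say in words that the week-32 rule was not met, and no row says that it was met. The people left without a row are those who reached at least 10% loss at week 32 and were due to continue on LIRA to week 52. An adherence classification that omits them would leave their place in the 52-week per-protocol set to the programmer, in an open-label trial.

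The group matters for the per-protocol comparison of the primary outcome because people with at least 10% loss at week 32 are well placed to reach 15% at week 52. That is a reasonable assumption, not a documented figure: the split in the protocol's background section (24.2% of early responders against 1.8% of early non-responders reaching 15%) is by week-16 status.

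Separately, the 510-day fallback in 14.2 does not appear to follow from the 70% rule.

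**Working it through.** **Row coverage in 14.1.** Take each possible participant and apply the words and the bracket of each row together.

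| Participant | Row 1 | Row 2 | Row 3 words | Row 3 bracket | Result |
|---|---|---|---|---|---|
| Week 16 below 5% or not measured | yes | no | no | not relevant | row 1 |
| Week 16 at least 5%; week 32 below 10% or not measured | no | yes | yes | no | row 2 only |
| Week 16 at least 5%; week 32 at least 10% | no | no | no | yes | no row |

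Row 3 needs its words and its bracket to hold at once, which is impossible, so it is empty. The third type of participant is unclassified. The second type stays in row 2, because the bracket in row 3 shuts them out.

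**Check against 14.2.** Replacing *did not meet* by *did meet* in row 3 makes its words agree with its bracket, its week-52 denominator and rows 3 and 4 of 14.2. Every participant then falls in exactly one row.

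**Fallback cut-offs.** Inputs: the threshold of at least 70% (SAP 2.2.1) and the week numbers in Appendix 7. Planned days = 7 × weeks. The not-adherent limit is the largest whole number of days strictly below 0.70 × planned days.

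| Week | Planned days | 70% | Limit by the rule | Limit in SAP |
|---|---|---|---|---|
| 16 | 112 | 78.4 | 78 | 78 |
| 32 | 224 | 156.8 | 156 | 156 |
| 52 | 364 | 254.8 | 254 | 254 |
| 104 | 728 | 509.6 | 509 | 510 |

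The first three figures reproduce. The fourth is one day too high: 510/728 = 70.05%, which meets the 70% threshold but is classed as not meeting it.

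**Other conventions tried.**

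- Rounding 70% to the nearest day gives 510 at week 104, but 157 at week 32 and 255 at week 52.
- A 730-day base gives 0.7 × 730 = 511, so a limit of 510. The matching 365-day base gives 0.7 × 365 = 255.5, so 255 at week 52, not 254.

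No single convention tried gives 78, 156, 254 and 510 together.

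**The case against.** The strongest reply is that the intent is plain. The bracket, the week-52 denominator, the existence of row 2 for week-32 failures, the wording of 14.2 and the opening sentence of Appendix 7 (doses count while the rules to continue are met) all point the same way. A programmer who codes the numeric brackets classifies everyone correctly. This stands: it is a recoverable wording error, not a missing rule. It does not remove the need to correct the text, because the row is an operative definition and its words say the opposite of what is meant.

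The reach is also limited. SAP 5.4.1 bases the primary analysis on complete cases. The per-protocol analysis is secondary (5.4.2), with one exploratory repeat (5.4.4). This too stands.

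A reader might go further and infer that people who failed at week 32 match both row 2 and row 3, and so might need 255 days instead of 157. The documents do not support that. Row 3 carries the bracket of at least 10%, which such people cannot satisfy; the overlap appears only if the bracket is ignored.

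On the 510-day figure, the reply is that it is a one-day difference in an approximation used only when a date is missing. SAP 5.5.1 restricts secondary outcomes to complete cases, so 14.2 appears to feed no modelled per-protocol comparison and mainly serves the descriptive 104-week adherence count. That is correct, and the point is minor.

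**Conclusion.** The concern holds as an internal contradiction in row 3 of 14.1. Taken literally, the row is empty and participants who met both the week-16 and week-32 rules have no 52-week adherence classification.

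It affects the secondary and exploratory per-protocol analyses of the primary outcome and the 52-week adherence endpoint. It does not affect the primary complete-case analysis, the ITT analysis or the sample size. The number of people concerned cannot be stated, because the documents give no expected proportion continuing past week 32. The practical effect is nil if the programmer follows the bracket, and loss of the whole group from the 52-week per-protocol set if the wording is followed and unclassified people are dropped.

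The 510-day cut-off is inconsistent with the SAP's own 70% rule by one day. Its effect is negligible: it needs a participant who met all three rules, has no week-104 date and has exactly 510 days on drug.

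**What to change.** In SAP 14.1, row 3, change *did not meet* to *did meet* for the week-32 rule, leaving the bracket, the denominator and the 254-day fallback as they are.

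In the same edit, in 14.2, row 4, change the missing-date cut-offs from at most 510 / more than 510 to at most 509 / more than 509.

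The cost is one word and two numbers. The copy reviewed is marked version 1.1 draft, and SAP section 1 provides for finalisation before database lock, so the correction fits there. Both edits concern how participants are classified for analysis; neither changes a dose or a stopping rule.
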